17.6.5 Questionnaires

17.6.5.1 Meal pattern questionnaire

For each treatment group, the absolute and percent change from baseline in total score of the Meal pattern questionnaire will be calculated and analysed using the Wilcoxon Rank Sum test at each visit. The absolute change for each question will be compared between the treatment groups by using the Wilcoxon Rank Sum test.

CONFIDENTIAL 84 (92)

Clinical Study Protocol EP-002 Final version v3.0 12NOV2020

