9.5 Exclusion criteria

Patients must not enter the study if any of the following exclusion criteria are fulfilled:

- 1. T2DM treated with medication.
- 2. History of any clinically significant disease or disorder which, in the opinion of the Investigator, may either put the patient at risk because of participation in the study, or influence the results or the patient's ability to participate in the study.
- 3. Any clinically significant illness, medical/surgical procedure or trauma within 4 weeks prior to the first administration of IMP, at the discretion of the Investigator.
- 4. Any planned major surgery within the duration of the study.
- 5. Untreated high blood pressure (systolic blood pressure [SBP] > 160 mmHg and diastolic blood pressure [DBP] >100 mmHg at screening).
- 6. Use of any of the prohibited medication listed in Table 9.6-1 within 2 weeks prior to the first administration of IMP. Recently started use of anti-depressants (*e.g.*, selective serotonin re-uptake inhibitors [SSRI]) within 2 weeks prior to the first IMP administration or planned start of anti-depressant treatment during the study period is not allowed, yet patients that are on stable treatment with anti-depressants for at least two months can be included.
- 7. Known hypersensitivity to any of the test substances. History of hypersensitivity to drugs with a similar chemical structure or class to orlistat and acarbose.
- 8. Gastrointestinal problems/diseases, *e.g.*, inflammatory bowel diseases and Irritable Bowel Syndrome (IBS). Untreated gastroesophageal reflux disease (GERD) or GERD that is treated occasionally is allowed as judged by the Investigator.
- 9. Cholestasis.
- 10. Previous gastrointestinal surgery that might influence gastrointestinal function significantly, previous bariatric surgery, and previous gallbladder surgery as judged by the investigator.
- 11. Known vitamin B12 deficiency or other signs of achlorhydria.
- 12. Chronical malabsorption syndrome.
- 13. Clinically significant abnormal laboratory values at screening as judged by the investigator.
- 14. History of severe allergic, cardiac or hepatic disease. History of significant cardiovascular disease such as myocardial infarction, congestive heart failure, stroke, serious cardiac arrhythmias. History of angina within 6 months prior to screening.
- 15. A personal or family history of Medullary Thyroid Carcinoma (MTC).
- 16. A personal or family history of Multiple Endocrine Neoplasia syndrome type 2 (MEN 2).

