11.5.4.1 Meal pattern questionnaire

The questionnaire for intake of meals consists of five multiple choice questions about dietary habits, in which each question contains 4 options to select from. For each question, a score (0-3 points) is obtained.

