11.5.4.2 Gastrointestinal tolerability questionnaire

The GSRS consists of 15 questions about gastrointestinal symptoms such as abdominal discomfort, heart burn, acid reflux, stomach rumbling, flatulence, constipation and diarrhoea. The questions need to be answered on the following scale: no discomfort at all, minor discomfort, mild discomfort, moderate discomfort, moderately severe discomfort, severe discomfort, very severe discomfort.

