17.1 General

Continuous data will be presented in terms of evaluable and missing observations, arithmetic mean, standard deviation (SD), median, minimum and maximum value.

Categorical data will be presented as counts and percentages. When applicable, summary data will be presented by treatment, and by assessment time. Individual patient data will be listed by patient number, treatment, and, where applicable, by assessment time.

All descriptive summaries and statistical analyses will be performed using SAS Version 9.4 or later (SAS Institute, Inc., Cary, NC).

Baseline will be defined as the visit with last data collection point prior to the first administration of IMP.

Outliers will be included in summary tables and listings and will not be handled separately in any analyses. No imputation of data will be performed neither for dropouts nor for missing data. An analysis of dropouts will be performed as detailed in Section 17.6.6.

All hypothesis testing will use a significance level of 5%.

Comparisons will be made pairwise and analysed at each visit if not stated otherwise.

CONFIDENTIAL 81 (92)

17.2 **Determination of sample size**

The hypothesis is to show that patients treated with EMP16-02 have a greater relative change (reduction) in body weight compared to placebo. The estimated treatment difference should be 5% with a standard deviation of 8%, a power of 80% and a significance level of 5% based on two-sided hypothesis testing. Using PASS V16.0 (method compare means), the number of evaluable patients needed per treatment arm is calculated to 41 patients. An evaluable patient is defined as a patient who has completed 26 weeks of treatment with IMP. Taking into account an estimated drop-out frequency of 20%, a total of 156 patients need to be randomised.

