17.6.5.2 Gastrointestinal tolerability questionnaire

For each treatment group, the absolute and percent change from baseline in total score of the GSRS be calculated and analysed using analysis of covariance with at least treatment, weight at baseline as covariates. More covariates will be addressed in the SAP.

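### Percent change in the meal-pattern total is undefined at a zero baseline, and in the GSRS total it depends on a scale origin the protocol does not state

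*Protocol*

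**What the plan says.** For the meal-pattern questionnaire, section 17.6.5.1 plans to analyse "the absolute and percent change from baseline in total score of the Meal pattern questionnaire" by Wilcoxon rank sum test at each visit, and also tests the absolute change question by question. Section 11.5.4.1 describes the instrument: "The questionnaire for intake of meals consists of five multiple choice questions about dietary habits", and "For each question, a score (0-3 points) is obtained".

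For GSRS, section 17.6.5.2 has "the absolute and percent change from baseline in total score of the GSRS be calculated and analysed using analysis of covariance", adjusting at least for treatment and baseline weight and leaving further covariates to the SAP. Section 11.5.4.2 says "The GSRS consists of 15 questions about gastrointestinal symptoms" and gives the answer scale in words only: "no discomfort at all, minor discomfort, mild discomfort, moderate discomfort, moderately severe discomfort, severe discomfort, very severe discomfort".

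Section 17.1 adds "No imputation of data will be performed neither for dropouts nor for missing data". The protocol gives no rule for a baseline of zero.

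**The concern.** Percent change needs a true, non-zero starting value. A sum of ordinal item scores has neither guarantee: it may be zero, and its origin is a coding convention.

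The meal-pattern total can be zero on the protocol's own scoring. The GSRS total can be zero or not, depending on a coding the protocol does not give. In either case the percentage attached to a given set of answers changes with the origin, so the two planned analyses of the same answers could disagree for that reason alone.

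This matters more for GSRS than for a routine questionnaire. Table 7.4-1 lists it as the assessment for GI tolerability. Section 11.6.1.1 keeps the expected GI symptoms out of adverse event reporting unless they are severe, so mild and moderate GI effects are captured systematically only by GSRS.

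**Working it through.** The protocol gives no figure for these analyses to reproduce. Its 41 evaluable patients per arm concern body weight and do not enter here.

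**Formula.** Percent change = 100 × (follow-up − baseline) / baseline.

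**Meal pattern.** Inputs from section 11.5.4.1: five items, each 0 to 3. Taking the total as the sum, it runs from 5 × 0 = 0 to 5 × 3 = 15.
- Baseline 0: the denominator is 0 and percent change does not exist.
- 1 to 2: 100 × 1/1 = +100%.
- 10 to 11: 100 × 1/10 = +10%, for the same one-point rise.

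**GSRS.** Inputs from section 11.5.4.2: 15 items, seven categories. Both codings are assumptions. Coded 0–6, the total runs from 0 to 90. Coded 1–7, it runs from 15 to 105, which is the first total plus 15. The same three-point worsening gives:

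| Total coded 0–6 | Percent change | Total coded 1–7 | Percent change |
|---|---|---|---|
| 0 to 3 | undefined | 15 to 18 | 3/15 = +20.0% |
| 1 to 4 | 3/1 = +300% | 16 to 19 | 3/16 = +18.8% |
| 3 to 6 | 3/3 = +100% | 18 to 21 | 3/18 = +16.7% |
| 10 to 13 | 3/10 = +30% | 25 to 28 | 3/25 = +12.0% |

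The absolute change is +3 in every cell.

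**Order of the arms.** Suppose patients in arm 1 go from 3 to 6 and in arm 2 from 15 to 24 (0–6 totals).
- Coded 0–6: 3/3 = 100% against 9/15 = 60%, so arm 1 looks worse.
- Coded 1–7: 3/18 = 16.7% against 9/30 = 30.0%, so arm 2 looks worse.
- Absolute change: +3 against +9 under both codings.

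**Illustrative power.** All inputs are assumptions: gamma-Poisson totals with gamma shape about 1.5, 45 patients per arm, a true worsening of 4 points, and a follow-up rate of 0.6 × own rate + 0.4 × a new draw + effect. There were 4,000 trials per scenario. Every model includes treatment, and the covariate is body weight except in the last row.

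| GSRS analysis | Mean baseline 8 | Mean baseline 12 |
|---|---|---|
| Percent change, coded 0–6 | 60% | 36% |
| Percent change, coded 1–7 | 94% | 73% |
| Absolute change | 91% | 69% |
| Absolute change, baseline GSRS total as covariate | 99% | 89% |

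An independent repeat agreed within 1 percentage point. With gamma shape between 1 and 3, percent change at mean baseline 8 had power 57–66% coded 0–6 and 90–96% coded 1–7. With no treatment effect, rejection was near 5% for every version (3–7%).

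**Patients lost under 0–6 coding.** With mean m and shape k, the share at zero is (k/(k+m))^k.
- m = 8, k = 1.5: (1.5/9.5)^1.5 = 6%.
- m = 8, k = 1: 1/9 = 11%.
- m = 8, k = 8: (8/16)^8 = 0.4%.
- m = 4, k = 1.5: (1.5/5.5)^1.5 = 14%.

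**Disagreement between codings.** The two codings differed on significance in 30–41% of the trials with a true effect in the setting above. They differed in about 2% in another setting (mean baseline 4, +3 points, 52 per arm), where both had very high power (97.9% and 99.9%). The rate depends on the scenario.

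**The case against.** The strongest objection is that the GSRS half rests on a coding the protocol does not adopt. A reader might infer that the plan, as written, loses symptom-free patients from the GSRS analysis and has only 60% power. The document does not support that. Item codes are ordinary SAP content. Coded 1–7, the lowest total is 15, nobody is lost, and percent change performs about as well as absolute change (94% against 91%, 73% against 69%). This stands, and the loss and low power must be stated as conditional on coding from 0. What survives is that an SAP coding rule would settle which percentage is reported without making a percentage of an ordinal sum meaningful.

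For the meal pattern, the test is rank-based, so extreme percentages cannot dominate it, and only patients at exactly 0 are lost. A total of 0 needs the lowest score on all five questions. This also stands as a limit on size, but the measure remains undefined for those patients.

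A reader might expect low GSRS baselines because "Gastrointestinal problems/diseases" are excluded. That is an inference. The same criterion admits untreated or occasionally treated reflux disease, section 9.6.2 prohibits regular use of antacids and acid suppressants, and GSRS asks about heartburn and reflux.

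Finally, a reader might call the missing baseline GSRS covariate an error. It is not, because section 17.6.5.2 leaves further covariates to the SAP.

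**Conclusion.** The point holds in limited form. Percent change of the meal-pattern total is undefined at an attainable baseline, with no rule to handle it. Percent change of the GSRS total has a size, and possibly an ordering of arms, that depends on an unstated and arbitrary origin. Both measures are fixed in the protocol itself.

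The practical size is unknown for the meal pattern, because nothing says how often a baseline of 0 occurs. For GSRS it ranges from little (coded 1–7) to a substantial loss of power (coded 0–6), on assumed distributions. The harm is lost power and instability, not false positives. These are secondary analyses, absolute change is planned alongside, and neither the primary endpoint nor the sample size is affected. It is a minor improvement worth making.

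**What to change.** Delete percent change for the total score in sections 17.6.5.1 and 17.6.5.2, and analyse absolute change only. Absolute change is defined at every baseline and is the same under either GSRS coding. The cost is one supplementary summary for each questionnaire. No data are lost, and no endpoint in Table 7.4-1 needs rewording, since none calls for percent change in these totals.

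As a recommendation rather than a correction, name the baseline GSRS total as a covariate in the GSRS ANCOVA. Under the assumptions above this raised power from 91% to 99% at mean baseline 8, and from 69% to 89% at mean baseline 12.

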17.6.5.2 Gastrointestinal tolerability questionnaire

For each treatment group, the absolute and percent change from baseline in total score of the GSRS be calculated and analysed using analysis of covariance with at least treatment, weight at baseline as covariates. More covariates will be addressed in the SAP.

17.6.5.3 Satiety and craving

Satiety and craving as total score after 14 and 26 weeks of treatment with EMP16-02 (120 mg O/40 mg A and 150 mg O/50 mg A) as compared to placebo, corrected for hunger and craving after standardised breakfast at baseline will be analysed using the Wilcoxon Rank Sum test. Each individual question may be analysed, if so, will this be described in the SAP.

17.6.5.4 Activity and sleep questionnaire

The two questions included in the Activity and Sleeping questionnaire will be analysed pairwise at each visit using a Chi-square test without continuity correction and presented in frequency tables.

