To assess the effect of two different doses of EMP16-02 (120 mg O/40 mg A and 150 mg O/50 mg A) on blood pressure during a 26-week period of oral treatment as compared to placebo.	Relative (%) and absolute change from baseline in blood pressure after 14 and 26 weeks of treatment with EMP16-02 (120 mg O/40 mg A and 150 mg O/50 mg A) as compared to placebo.	Blood pressure measurement (Section 11.5.3)
To assess the effect of two different doses of EMP16-02 (120 mg O/40 mg A and 150 mg O/50 mg A) on quality of life during a 26-week period of oral treatment as compared to placebo.	Change from baseline in quality of life after 26 weeks of treatment with EMP16-02 (120 mg O/40 mg A and 150 mg O/50 mg A) as compared to placebo.	Health and life quality questionnaire RAND-36 (Section 11.5.4.5) Activity and sleep questionnaire (Section 11.5.4.4)
To assess the relationship between dropout(s) and tolerability for two different doses of EMP16-02 (120 mg O/40 mg A	Dropout rate (overall and GI-related) following treatment with EMP16-02 (120 mg O/40 mg A and 150 mg O/50 mg A) as compared to placebo.	Careful collection of reason for early discontinuation

CONFIDENTIAL 30 (92)

Clinical Study Protocol EP-002 Final version v3.0 12NOV2020

	Objective	Endpoint	Assessment(s)
	and 150 mg O/50 mg A) during a 26-week period of oral treatment as compared to placebo.		
	To assess the safety and GI tolerability of two different doses of EMP16-02 (120 mg O/40 mg A and	Frequency and severity of AEs during 26 weeks of treatment with EMP16-02 (120 mg O/40 mg A and 150 mg O/50 mg A) as compared to placebo.	AE questioning (Section 11.6.1)
	150 mg O/50 mg A) during a 26-week period of oral treatment as compared to placebo.	Clinically significant relative (%) and absolute changes from baseline in safety laboratory parameters and electrocardiogram (ECG) after 26 weeks of treatment, and in vital signs after 7, 14 and 26 weeks of treatment with EMP16-02 (120 mg O/40 mg A and 150 mg O/50 mg A) as compared to placebo. GI tolerability after 2, 4, 6, 8, 14 and 26 weeks of treatment with EMP16-02 (120 mg O/40 mg A and 150 mg O/50 mg A) as compared to placebo.	Vital signs (Section 11.6.3) 12-lead ECG (Section 11.6.4) Blood sampling for assessment of safety laboratory parameters (Section 11.6.5) GSRS (gastrointestinal symptom rating scale, Section 11.5.4.2)

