11.5.4.4 Activity and sleep questionnaire

The activity and sleep questionnaire consists of 2 questions about physical activity and sleep during the previous day/night.

CONFIDENTIAL 60 (92)

pharma

Clinical Study Protocol EP-002 Final version v3.0 12NOV2020

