17.6.5.5 Health and quality of life (RAND-36)

The change from baseline in quality of life after 26 weeks of treatment with EMP16-02 (120 mg O/40 mg A and 150 mg O/50 mg A) as compared to placebo will be analysed using the Wilcoxon Rank Sum test.

17.6.6 **Drop-out rate**

The drop-out rate (overall and GI-related) following treatment with EMP16-02 (120 mg O/40 mg A and 150 mg O/50 mg A) as compared to placebo will be analysed using Chi-square test without continuity correction.

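### The two activity and sleep items are compared visit by visit with a Chi-square test that leaves out the Visit 2 answer and ignores any order in the answers

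*Protocol*

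**What the plan says.** Section 17.6.5.4 of the protocol states that the two questions "will be analysed pairwise at each visit using a Chi-square test without continuity correction and presented in frequency tables". It mentions neither baseline nor change and defers nothing to the SAP. The synopsis (Statistical methods) also names a Chi-square test for this questionnaire.

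On what is measured, Section 11.5.4.4 says only: "The activity and sleep questionnaire consists of 2 questions about physical activity and sleep during the previous day/night". It gives no response options, number of levels or score. Tables 8.1-3 and 11.5-2 schedule the questionnaire at Visits 2, 3, 4 and 5, so a baseline answer is collected.

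Table 7.4-1 names the questionnaire, next to RAND-36, as an assessment for this secondary endpoint: "Change from baseline in quality of life after 26 weeks of treatment with EMP16-02".

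For the single meal pattern items, Section 17.6.5.1 says: "The absolute change for each question will be compared between the treatment groups by using the Wilcoxon Rank Sum test". For RAND-36, Section 17.6.5.5 says that the change from baseline "as compared to placebo will be analysed using the Wilcoxon Rank Sum test".

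**The concern.** Two features of the planned test stand out.

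- **Baseline is unused.** The endpoint is a change from baseline and the Visit 2 answer is available, but the comparison uses only the answers given at the visit in question. Taken literally, testing at each visit would even include Visit 2, before any randomised dose.
- **Order is ignored.** A Pearson Chi-square treats the categories as interchangeable labels and spreads a shift in one direction over k − 1 degrees of freedom. If the items are graded, as questions on activity and sleep plausibly are, this wastes information.

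At stake is the chance of detecting a real shift in activity or sleep, and whether the reported p-value addresses the endpoint that the questionnaire is listed under.

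**Working it through.** **1. How the five questionnaires use baseline (protocol Section 17.6.5)**

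| Questionnaire | Quantity analysed | Test |
|---|---|---|
| Meal pattern (17.6.5.1) | change from baseline in total score; change per question | Wilcoxon Rank Sum |
| GSRS (17.6.5.2) | change from baseline in total score | analysis of covariance |
| Satiety and craving (17.6.5.3) | total score, corrected for baseline | Wilcoxon Rank Sum |
| RAND-36 (17.6.5.5) | change from baseline | Wilcoxon Rank Sum |
| Activity and sleep (17.6.5.4) | answer at the visit | Chi-square |

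Activity and sleep is the only one that does not use baseline, and no reason is given.

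**2. The plan's own sample size.** Section 17.2 assumes a difference of 5%, an SD of 8% and "a power of 80% and a significance level of 5% based on two-sided hypothesis testing". Normal approximation: n = 2 × (1.96 + 0.8416)² × 8² / 5² = 2 × 7.85 × 2.56 = 40.2, so 41 per arm. With 20% drop-out, 41 / 0.8 = 51.25, so 52 per arm and 3 × 52 = 156. The stated figures reproduce. They concern body weight: the protocol gives no effect size for activity or sleep, so the effects below are assumptions.

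**3. Cost of ignoring order.** Inputs: 41 per arm and two-sided 5% (Sections 17.1 and 17.2); number of levels, placebo distribution and odds ratio (OR) assumed. Active-arm probabilities come from a proportional-odds shift: each cumulative odds c/(1 − c) is divided by the OR.

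Example: four equally likely levels, OR 2.5. Cumulative odds 0.333, 1 and 3 become 0.133, 0.4 and 1.2. The cumulative probabilities become 0.118, 0.286 and 0.545, so the level probabilities are 0.118, 0.168, 0.260 and 0.455 (differences of unrounded values).

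Power from 20,000 simulated trials per cell, uncorrected Chi-square → tie-corrected Wilcoxon on the visit answer, baseline used in neither (equally likely placebo answers):

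| Levels | OR 2 | OR 2.5 | OR 3 |
|---|---|---|---|
| 2 | 35.3% → 35.3% | 53.1% → 53.1% | 66.6% → 66.6% |
| 3 | 30.9% → 39.1% | 48.9% → 59.2% | 64.5% → 74.5% |
| 4 | 26.7% → 40.3% | 44.6% → 62.4% | 60.6% → 77.3% |
| 5 | 24.0% → 41.7% | 40.7% → 63.2% | 56.6% → 78.7% |

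With skewed or centred placebo distributions included, the loss over 3 to 5 levels and OR 2 to 3 runs from 8.0 to 23.5 points. Outside that grid it is 3 to 7 points at OR 1.5 and 6 to 16 at OR 4 (both 3 to 5 levels), and 22 to 31 with 7 levels at OR 2 to 3. With no effect and 3 to 5 levels, both tests rejected in about 5% of trials.

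Asymptotic check: a noncentrality of (1.96 + 0.84)² ≈ 7.85 gives 80% power on 1 df but 71%, 64% and 60% on 2, 3 and 4 df.

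**4. Effect of using the Visit 2 answer.** Latent normal baseline and follow-up, shift 0.6 SD, 41 per arm, 3,000 replicates. Rank analysis of covariance stands in for the baseline-adjusted ordinal model.

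| Levels | Baseline correlation | Chi-square at visit | Wilcoxon on raw change | Baseline-adjusted rank analysis |
|---|---|---|---|---|
| 3 | 0.2 | 57.6% | 43.4% | 67.0% |
| 3 | 0.5 | 56.3% | 54.6% | 71.8% |
| 3 | 0.7 | 56.5% | 69.0% | 81.4% |
| 4 | 0.2 | 51.3% | 43.0% | 69.7% |
| 4 | 0.5 | 51.7% | 60.4% | 76.8% |
| 4 | 0.7 | 52.1% | 77.9% | 88.2% |

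With two levels, a separate run of the same design gave 57–59% for Chi-square and 57–67% for the adjusted analysis: a gain of about 0 to 8 points, rising with the correlation. Type I error was near 5% for both.

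**The case against.** The strongest reply is that the protocol never says the answers are ordered. The three instruments described just before this one each get a stated scale (Sections 11.5.4.1 to 11.5.4.3); this one does not. A continuity correction is normally a matter for 2 × 2 tables, and the protocol uses the same phrase for binary outcomes such as weight-loss responders and drop-out. Yes/no items are therefore quite possible, and then nothing is lost through order. This stands, and it makes the order part of the point conditional. The phrase does not settle the format, because Section 17.6.3 also uses it for diabetic and prediabetic status.

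Four stronger readings are tempting, and the protocol does not support them:

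- *The test is invalid.* Under randomisation, a week-26 comparison between arms is a valid test of treatment, and its type I error is close to nominal.
- *Ordered answers alone imply an 8 to 23 point loss.* That range also needs 3 to 5 levels and an odds ratio of about 2 to 3, and the protocol gives neither.
- *The quality-of-life endpoint has no matching analysis.* RAND-36 is analysed as change from baseline in Section 17.6.5.5. Activity and sleep is a two-item form beside a 36-item one.
- *A significant result could not be interpreted.* The same sentence of Section 17.6.5.4 requires frequency tables, which would show the direction.

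Nor would copying the meal pattern method be a safe repair. The items ask about a single day and night, so a low correlation over 26 weeks is plausible. In that case Wilcoxon on the raw change can have less power than the planned test (43.4% against 57.6% with three levels at correlation 0.2).

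**Conclusion.** The point holds as a minor matter of efficiency and endpoint alignment. Whatever the answer format, the planned test leaves out a baseline answer that is collected and that the endpoint in Table 7.4-1 calls for, and this questionnaire is the only one of the five handled that way. The loss from ignoring order is about 8 to 23 points of power if there are 3 to 5 ordered levels, a proportional odds ratio of about 2 to 3 and 41 patients per arm. It is zero for yes/no answers. Under the latent-normal assumptions above, a baseline-adjusted analysis gains about 9 to 36 points over the plan with 3 or 4 ordered levels (67.0 − 57.6 = 9.4; 88.2 − 52.1 = 36.1) and about 0 to 8 points with two. The matter touches one supporting assessment of a secondary endpoint in a trial that calls itself exploratory. It has no bearing on the primary analysis.

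**What to change.** In Section 17.6.5.4 and the synopsis:

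- State the response options of both questions.
- Compare each active arm with placebo at the post-baseline visits, with week 26 as the comparison for the endpoint, in a model containing treatment and the Visit 2 answer. Use proportional odds if the item is ordered and logistic regression if it is yes/no.
- Keep the frequency tables as the descriptive display.
- Do not substitute a Wilcoxon test on the raw change score.

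The cost is a change of wording and a different SAS procedure on data already collected, with no extra patients or visits. The small downside is less power for a difference that does not run in one direction across the categories, which the frequency tables would still show.
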